been shown to reduce hyperglycaemia in patients with type 2 diabetes mellitus (T2DM). The mechanisms of action for liraglutide include stimulation of insulin secretion and decrease of glucagon secretion, both in a physiological and glucose dependent-manner. The effects of liraglutide also include reduced sensation of hunger and increased satiety, leading to decreased food intake and subsequent weight loss.

Victoza[®] is indicated for the treatment of adults with T2DM at doses of 1.2 mg and 1.8 mg, and received marketing authorisation from the European Medicines Agency (EMA) in June 2009. Saxenda[®] (liraglutide 3.0 mg) is indicated as an adjunct to a reduced-calorie diet and increased physical activity for weight management in adults who are obese, or adults who are overweight with at least one weight-related comorbidity. The efficacy of Saxenda[®] was demonstrated in five phase 2 and 3 clinical trials involving around 5,800 obese/overweight patients, which showed that more patients administered Saxenda[®] achieved clinically relevant weight loss than those treated with placebo. Saxenda[®] received marketing authorisation from the EMA in March 2015.

As defined in the Risk Management Plan (RMP) for Saxenda[®], a retrospective drug utilisation study (DUS) to investigate patterns of use of Saxenda[®] and Victoza[®] in routine clinical practice has been requested by the EMA as a post marketing requirement. As is the case with any medicinal product, real-world use of Saxenda[®] or Victoza[®] may differ from the approved indication or recommendations outlined in the Summary of Product Characteristics (SmPC) (1, 2). Considering that these two liraglutide products with the same strength and formulation will be available for different indications with different doses, there is the potential for inadvertent use of one or the other product for either indication. The DUS will allow assessment of usage patterns of liraglutide for weight management, and thereby could refine pharmacovigilance planning and risk management.

7 Research question and objectives

The aim of this study is to investigate in-market utilisation of liraglutide for weight management. Specifically, the primary and secondary objectives are the following:

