7.1 Primary objective

To assess the use of Saxenda® according to the approved indication:

Saxenda is indicated as an adjunct to a reduced-calorie diet and increased physical activity for weight management in adult patients with an initial Body Mass Index (BMI) of

• $\geq 30 \text{ kg/m}^2 \text{ (obese), or}$

Protocol		Date:	23 November 2015	Novo Nordisk
Study ID: NN8022-4241		Version:	5.0	
UTN: U1111-1185-3661		Status:	Final	
EU PAS No.:	CONFIDENTIAL	Page:	16 of 53	

• ≥ 27 kg/m² to < 30 kg/m² (overweight) in the presence of at least one weight-related comorbidity such as dysglycaemia (pre-diabetes or type 2 diabetes mellitus), hypertension, dyslipidaemia or obstructive sleep apnoea.

Treatment with Saxenda should be discontinued after 12 weeks on the 3.0 mg/day dose if patients have not lost at least 5% of their initial body weight.

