7.3 Endpoints

Primary endpoint:

The following endpoints will address the primary objective (concerning Saxenda® only):

BMI and comorbidities:

- Number of patients with Body Mass Index (BMI)≥30 kg/m² (measured less than 6 months before date of first prescription).
- Number of patients with 27 kg/m² ≤BMI<30 kg/m² (measured less than 6 months before date of first prescription) and
 - ≥1 relevant comorbidity registered:
 - Dysglycaemia (T2DM or prediabetes), hypertension, dyslipidaemia, and/or obstructive sleep apnoea.
 - o No relevant comorbidities (described above) registered.
- Number of patients with BMI<27 kg/m² (measured less than 6 months before date of first prescription).
- Number of patients with BMI not measured within 6 months before date of first prescription.

 Protocol
 Date:
 23 November 2015
 Novo Nordisk

 Study ID: NN8022-4241
 Version:
 5.0

 UTN: U1111-1185-3661
 Status:
 Final

 EU PAS No.:
 CONFIDENTIAL
 Page:
 17 of 53

Stopping rule:

- Number of patients with at least 5% weight loss (measured 16-24 weeks after first prescription date) and continuing treatment.
- Number of patients with less than 5% weight loss (measured 16-24 weeks after first prescription date) and continuing treatment.
- Mean weight loss (measured 16-24 weeks after first prescription date) in patients not treated according to stopping rule.

Secondary endpoint:

The following endpoint will be used to address the first secondary objective (concerning Victoza[®] only):

- Number of patients with Victoza[®] prescriptions fulfilling at least one of the following criteria:
 - 1. Dose information of 3.0 mg per day, or
 - 2. Indication of weight management.

The following endpoints will be used to address the second secondary objective (concerning Saxenda® only):

- Adherence to dose escalation according to label:
 - o Number of patients who have reached a dose of 3.0 mg within 4-12 weeks after first prescription date.
- Concomitant medication with of other GLP-1 receptor agonists:
 - Number of Saxenda[®] patients with other GLP-1 receptor agonists prescribed during continued treatment with Saxenda[®] (continued treatment is defined as no gaps between prescriptions of more than 90 days, identified by examining repeat prescription dates).
- Duration of treatment with Saxenda®:
 - o Number of patients with a treatment duration of:

Protocol		Date:	23 November 2015	Novo Nordisk
Study ID: NN8022-4241		Version:	5.0	
UTN: U1111-1185-3661		Status:	Final	

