8.2.6 Flowchart

The data collection period for Saxenda[®]/Victoza[®] will be the interval between the launch date of Saxenda[®] to the index date of the pilot or full study, respectively. Table 1 and Table 2 show the data to be collected respectively for Saxenda[®] and Victoza[®] patients at different time points in relation to initiation of treatment. Data collection will encompass the following treatment periods for Saxenda[®]: (1) a time frame of 6 months prior to treatment initiation, (2) treatment initiation, (3) 4-12 weeks post treatment initiation, (4) 16-24 weeks post treatment initiation, and also (5) throughout the entire treatment period. Data collection will encompass the following treatment periods for Victoza[®]: (1) treatment initiation, and (2) throughout the entire treatment period.

Protocol	UTN: U1111-1185-3661	Date:	23 November 2015	Status:	Final	Novo Nordisk
Study ID: NN8022-4241	EU PAS No.:	Version:	5.0	Page:	23 of 53	

Table 1 - Saxenda® patients¹

Weeks in relation to initiation of treatment/time of first prescription	Prior to treatment initiation	0	4 – 12 weeks	16 – 24 weeks	Throughout the treatment period ²
Visit window			+4 weeks	+4 weeks	
Demography ³		X			
Co-morbidities ⁴	X				
Body Weight		X^5		X^6	
Adult height	X				
BMI		X^5			
Brand name		X			
Indication prescribed		X			
Target dose prescribed		X			
Current dose ⁷			X	X	
Treatment start date		X			
Treatment stop date					X
Concomitant medication with GLP-1					
receptor agonists					X
(Brand name and start date)					

- 1) Inclusion criteria must be fulfilled (incl. obtained informed consent) before data extraction is performed
- 2) Censoring at 24 months after launch
- 3) Sex, age
- 4) Diagnosis of or treatment of pre-diabetes, type 2 diabetes mellitus (T2DM), hypertension, dyslipidaemia and/or obstructive sleep apnoea.
- 5) Latest recording within 6 months before first prescription of Saxenda®
- 6) If not available the earliest subsequent body weight and date of measurement should be recorded
- 7) If treatment discontinuation occurs prior to/between the specified time points, the dose of Saxenda® at time of treatment discontinuation should be recorded.

Protocol		Date:	23 November 2015	Novo Nordisk
Study ID: NN8022-4241		Version:	5.0	
UTN: U1111-1185-3661		Status:	Final	
EU PAS No.:	CONFIDENTIAL	Page:	24 of 53	

Table 2 - Victoza® patients¹

Weeks in relation to initiation of treatment/time of first prescription	0	Throughout the treatment period ²

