- HbA1c 5.7-6.4% (both inclusive)

T2DM:

- FPG \geq 126 mg/dL (7.0 mmol/L) and/or
- 2 hour post-challenge (during an OGTT) plasma glucose ≥ 200 mg/dL (11.1 mmol/L) and/or
- HbA1c > 6.5%
- O Diagnosis of obstructive sleep apnoea may be based on treatment with continuous positive airway pressure (CPAP) device.
- Concomitant medication with other GLP-1 receptor agonists (brand name and start date).
- Dose at 4-12 weeks and 16-24 weeks post initiation of treatment
- Body weight at 16-24 weeks post initiation of treatment. If body weight is not available within this interval, the earliest subsequent body weight and date of measurement should be recorded

Victoza® initators only:

• Dose throughout the treatment period

 Protocol
 Date:
 23 November 2015
 Novo Nordisk

 Study ID: NN8022-4241
 Version:
 5.0

 UTN: U1111-1185-3661
 Status:
 Final

 EU PAS No.:
 Page:
 26 of 53

Prescription outside label

Prescription outside label will be categorised as follows:

Saxenda® patients:

- BMI<27 kg/m² within 6 months before date of first prescription
- 27 kg/m² ≤BMI < 30 kg/m² within 6 months before date of first prescription and no relevant comorbidities registered (dysglycaemia [T2DM or prediabetes], hypertension, dyslipidaemia, and/or obstructive sleep apnoea)
- BMI not measured within 6 months before date of first prescription
- Non-adherence to dose escalation according to SmPC (i.e., daily dose of 3.0 mg not reached within 4-12 weeks post initiation of treatment)
- Non-adherence to stopping rule (i.e., less than 5% weight loss after 16-24 weeks on Saxenda[®] 3.0 mg and still on continued treatment)
- Concomitant medication with other GLP-1 receptor agonists

Victoza® patients:

- Dose of 3.0 mg per day
- Prescribed indication of weight management

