8.7.2 Statistical methods

Details of the data analyses, along with table, listing and figure (TLF) templates, will be fully described in a Statistical Analysis Plan (SAP).

In brief, the descriptive analyses will present Saxenda[®] and Victoza[®] utilisation by indication. Results will be evaluated by site characteristics, including country and geographic region within country, to ascertain any patterns of prescribing by specific indication. The main analysis will be to estimate the proportion of prescriptions outside label among Saxenda[®] or Victoza[®] patients during the entire study period in the countries of interest. The proportion of each of the forms of prescription outside label will be described (see section on prescription outside label). Characteristics of patients prescribed Saxenda[®] or Victoza[®] according to the respective approved SmPCs will also be evaluated.

Analyses on the following will be conducted:

Site characteristics

Descriptive statistics will be provided for the following variables:

- Geographic location of physician site (number and proportion)
- Specialty or area of primary practice (e.g. GPs, cardiologists, endocrinologists (or other diabetes and obesity specialists), etc.) (number and proportion)
- Practice type (e.g. community hospital, academic/medical centre, office based, etc.) (number and proportion)
- Number of physicians who practice at site (mean, standard deviation, median, first and third quartiles and range)
- Patient volume (i.e. number of patients and estimated number of patients using Victoza[®] or Saxenda[®]) (mean, standard deviation, median, first and third quartiles and range)

Patient demographics, medical history, and other characteristics:

Descriptive statistics will be provided for the following variables:

- Age (mean and standard deviation; number and proportion for age categories)
- Sex (number and proportion)

Protocol		Date:	23 November 2015	Novo Nordisk
Study ID: NN8022-4241		Version:	5.0	
UTN: U1111-1185-3661		Status:	Final	
EU PAS No.:	CONFIDENTIAL	Page:	30 of 53	

Drug utilisation:

Descriptive statistics will be provided for the following variables:

Saxenda® or Victoza® patients:

- Brand name (number and proportion)
- Indication prescribed at treatment initiation (number and proportion)
- Target dose prescribed at treatment initiation (number and proportion for target dose categories: 3.0 mg/day (for Saxenda® patients) and 1.2 mg/day, 1.8 mg/day or 3.0 mg/day (for Victoza® patients)

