Saxenda® patients only:

- Comorbidities:
 - Dysglycaemia (T2DM or prediabetes), hypertension, dyslipidaemia, and/or obstructive sleep apnoea (number and proportion)
- Dose at 4-12 weeks and 16-24 weeks post initiation of treatment (mean, standard deviation)
- Duration of treatment (or ongoing treatment) (mean, standard deviation, median, first and third quartiles and range; number and proportion for treatment completion: completed treatment or ongoing treatment)

Victoza® patients only:

- Increase in Victoza® dose to 3.0 mg/day (number and proportion)
- Prescription of Victoza® for weight management (number and proportion)

Prescription outside label:

Descriptive statistics for the following:

Saxenda® patients:

- BMI<27 kg/m² (number and proportion)
- 27 kg/m²≤BMI<30 kg/m² and no relevant comorbidities registered (dysglycaemia (T2DM or prediabetes), hypertension, dyslipidaemia, and/or obstructive sleep apnoea) (number and proportion)
- BMI not measured within 6 months before date of first prescription (number and proportion)
- Non-adherence to dose escalation according to label (i.e., 3.0 mg not reached within 4-12 weeks after date of first prescription) (number and proportion)
- Non-adherence to stopping rule (i.e., less than 5% weight loss after 16-24 weeks on Saxenda® 3.0 mg and still on continued treatment) (number and proportion)

Protocol		Date:	23 November 2015	Novo Nordisk
Study ID: NN8022-4241		Version:	5.0	
UTN: U1111-1185-3661		Status:	Final	
EU PAS No.:	CONFIDENTIAL	Page:	31 of 53	

• Concomitant medication with other GLP-1 receptor agonists (brand name) (number and proportion)

Victoza® patients:

- Dose information of 3.0 mg per day (number and proportion)
- Prescribed indication of weight management (number and proportion)

All analyses will be performed using SAS 9.2 (or higher) statistical software (SAS Institute Inc., Cary, North Carolina, USA). Programs, logs, and output will be reviewed for accuracy according to relevant standard operating procedures.

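### The outside-label rule for BMI 27 to <30 closes a comorbidity list that the quoted indication leaves open, so patients with only another weight-related comorbidity are counted as outside label

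*Protocol*

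**What the plan says.** Section 7.1 (and the summary in 3.3) quotes the indication. For overweight patients it applies "in the presence of at least one weight-related comorbidity such as dysglycaemia (pre-diabetes or type 2 diabetes mellitus), hypertension, dyslipidaemia or obstructive sleep apnoea". Section 6 restates it with no list at all, as "adults who are overweight with at least one weight-related comorbidity".

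The primary endpoint in section 7.3 divides the BMI 27 to <30 band in two: at least one relevant comorbidity, spelled out as the four conditions, or "No relevant comorbidities (described above) registered".

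Section 8.3, under prescription outside label, places the second group outside label and repeats the four: "no relevant comorbidities registered (dysglycaemia [T2DM or prediabetes], hypertension, dyslipidaemia, and/or obstructive sleep apnoea"). Section 8.7.2 does the same in its analysis list: "no relevant comorbidities registered (dysglycaemia (T2DM or prediabetes), hypertension, dyslipidaemia, and/or obstructive sleep apnoea").

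The data to be abstracted follow the same list. Footnote 4 to Table 1 (section 8.2.6) reads "Diagnosis of or treatment of pre-diabetes, type 2 diabetes mellitus (T2DM), hypertension, dyslipidaemia and/or obstructive sleep apnoea". The comorbidity item in section 8.3 names the same conditions, and section 8.4 points to 8.3 for what will be collected.

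**The concern.** The primary objective is to assess use according to the approved indication, and section 8.7.2 builds its main result on that: "The main analysis will be to estimate the proportion of prescriptions outside label among Saxenda" or Victoza patients. In the 27 to <30 band, comorbidity alone decides whether the BMI part of the indication is met. There the rule is narrower than the wording it is meant to test.

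A patient with a recorded weight-related condition other than the four would be reported to the regulator as prescribed outside label although the quoted indication covers that patient. Because the other condition is not on the data list, a SAP could not put this right afterwards.

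**Working it through.** **Side by side.**

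| Place in protocol | Comorbidity requirement for BMI 27 to <30 | List |
|---|---|---|
| 3.3 and 7.1, indication | Any weight-related comorbidity, four named after 'such as' | Open |
| 6, background | Any weight-related comorbidity | No list |
| 7.3, primary endpoint | The four, or none of them | Closed |
| 8.3 and 8.7.2, outside label | None of the four means outside label | Closed |
| Table 1 footnote 4 and 8.3, data | The four | Closed |

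The protocol marks other lists as open with 'e.g.' (specialty and practice type in 8.3 and 8.7.2) but not this one. No reason for the narrowing is given, and the limitations in 8.9 do not mention it. The prescribed indication is collected, but nothing in the protocol uses it to recover other comorbidities.

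**Who is affected.** A patient must meet three conditions: BMI 27 to <30; none of the four registered; another weight-related comorbidity recorded. Patients with BMI of 30 or more, BMI below 27, no BMI measured in the window, or any of the four conditions are classified the same either way.

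**Size.** The protocol states no figure to reproduce. Its only usable number is n = 150 Saxenda patients in the full study (8.2.1). The other three inputs are assumptions:
- q, share of the 150 with BMI 27 to <30: 10% to 30%
- c, share of those with none of the four: 10% to 40%
- d, share of those with another weight-related comorbidity recorded: 10% to 50%

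Category count = n × q × c. Wrongly counted = n × q × c × d.

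| | q | c | d | In category | Wrongly counted | Points of 150 |
|---|---|---|---|---|---|---|
| Low | 0.10 | 0.10 | 0.10 | 1.5 | 0.15 | 0.1 |
| Middle | 0.20 | 0.25 | 0.30 | 7.5 | 2.25 | 1.5 |
| High | 0.30 | 0.40 | 0.50 | 18 | 9 | 6.0 |

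Within the category, the misclassified share is d whatever q and c are. The category is therefore inflated by 1/(1 − d): 1/0.9 = 1.11 at d = 10%, 1/0.7 = 1.43 at 30%, and 1/0.5 = 2 at 50%. The relative error depends entirely on an input that the documents do not supply.

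**The case against.** A fixed list of four conditions is a reasonable operational definition. Abstractors in two countries can apply it consistently, and the protocol defines no weight-related comorbidity beyond the four. The row spells out its definition each time, and 8.7.2 reports each form of outside-label use separately, so a careful reader can see what was counted. The counts in 7.3 are true counts of what they describe; the outside-label tag is added only in 8.3 and 8.7.2. All of this stands, and it confines the fault to what that row is taken to mean and to the data needed to check it. It does not justify the tag, because the quoted indication does not limit the comorbidities to four.

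The size may also be slight. As an illustration, a fall from 6 to 4 of 150 is 4.0% to 2.7%, or 1.3 points, while the exact 95% interval for 6/150 runs from 1.5% to 8.5%. That limits the weight of the point, though the error is systematic and a larger sample would not remove it.

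A remedy can also err the other way. Accepting any free-text condition as within label, with no criterion and after abstraction, could understate outside-label use. That is a sound objection to a simple reclassification and shapes the fix.

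A reader might infer that outside-label use as a whole is overstated. The documents do not support that. The upward direction is shown for this category only. The overall figure also draws on unmeasured BMI, dose escalation, the stopping rule and concomitant GLP-1 receptor agonists. Elsewhere the rule is looser than the indication: no category checks diet and physical activity, and treatment proxies are accepted as diagnoses.

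**Conclusion.** The rule is wrong as written, on a narrow point. It treats as exhaustive a list that the quoted indication gives as examples, and the data list prevents correction later. The error runs upward in one category. Under the assumed ranges it is 0.1 to 6.0 percentage points of 150 Saxenda patients, and 1.5 points at the middle values. If the overall proportion counts a patient once for any form of outside-label use, the effect on it is at most this, since some affected patients may already count for another reason.

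Two stronger statements are tempting. One is that every overweight patient with some other comorbidity is miscounted; only those with none of the four are. The other is that the category is overstated by half; that follows solely from assuming d = one third, since 1/(1 − 1/3) = 1.5, and nothing in the protocol supports that value.

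**What to change.** Add one CRF item: other weight-related comorbidity recorded (specify). Report the BMI 27 to <30 band in three rows:

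1. at least one of the four named conditions;
2. only another weight-related comorbidity;
3. none recorded.

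Name the category now planned in 8.3 and 8.7.2 'none of the four listed comorbidities'; it is rows 2 and 3 together, so the planned count is kept. Give the outside-label proportion both ways, with row 2 counted as outside label and with it not counted. Set the criterion for reviewing the free text before data abstraction starts, so that the classification does not depend on the results.

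The cost is one field, one table row, a written criterion and medical review of what should be a few entries. If the field cannot be added, rename the category and state in 8.9 that other weight-related comorbidities were not collected, so the row may include patients who meet the indication. That corrects the label but does not identify those patients.

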8.7 Data analysis

All data analysis will be performed by

As this is a descriptive study that will investigate in-market utilisation of liraglutide, no formal statistical testing will be conducted.

Characteristics of study participants will be reported as mean, standard deviation, median, first and third quartiles and range for continuous variables and as number and proportion of patients with observed (non-missing) data for categorical variables. Study participation will be presented, including number of sites approached for the study and response rate, by specialty, and number of patients approached, response rates, and reasons for refusal. Characteristics of the participating sites and patients will be presented, stratified by country. The data may also be evaluated and presented for other meaningful subgroups of patients (e.g., by sex or age). Comparison between participants and non-participants will be made for sites and patients. Participating and non-participating sites will be compared on geographic location, area of primary practice, practice type, practice size and

Protocol		Date:	23 November 2015	Novo Nordisk
Study ID: NN8022-4241		Version:	5.0	
UTN: U1111-1185-3661		Status:	Final	
FILPAS No.	CONFIDENTIAL	Page.	29 of 53	

patient volume. Comparison of participating patients and the total population of patients treated with Saxenda[®] or Victoza[®] will be made, subject to data availability.

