8.9 Limitations of the research methods

As this is a non-interventional study, potential bias cannot be ruled out.

Data collection will reflect routine clinical practice rather than mandatory ass

Data collection will reflect routine clinical practice rather than mandatory assessments at prespecified time points, which may have an impact on the amount of data available and its interpretation.

Biases

Selection bias

 Protocol
 Date:
 23 November 2015
 Novo Nordisk

 Study ID: NN8022-4241
 Version:
 5.0

 UTN: U1111-1185-3661
 Status:
 Final

Page:

35 of 53

In order to minimize selection bias, the sampling strategy that was designed for the proposed study, will truly reflect real-life clinical practice since it will capture all possible treatment settings. In addition, selection bias due to sampling and participation will be addressed by comparing selected characteristics of the study patients and prescribers with those recorded in an external national database (IMSLifeLink).

Information bias

EU PAS No .:

At the prescriber (site) level, information bias is mitigated by the retrospective design. This study involves no intervention and treatment of patients considered eligible and their medical records at a site have been completed prior to the country-specific index date. Thus, the knowledge about this study (and its conduct) will not have had impact on the standard medical care and Saxenda® or Victoza® prescription practices at a site and will not have affected the treatment of patients. Data collected from medical records will therefore reflect real world medical practice.

At the patient level, misclassification of drug exposure has to be considered. Medical records provide detailed information on prescribed and/or dispensed medications but may not contain information on the intended duration of use (days of supply) and often do not contain information on the actual use of the medications by the patient. Thus, patients may be classified as exposed to a drug although they actually have not taken the drug. For this reason, great care will be taken to ensure the quality of the information that is abstracted, and prescribers' follow-up by clinical research associates (CRAs) will be enforced.

Missing Data

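### Patients with no BMI recorded in the prior 6 months are classified as outside label, although their label status is unknown, which biases the overall outside-label proportion upward

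*Protocol*

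**What the plan says.** Section 8.3 introduces its list with "Prescription outside label will be categorised as follows". One of the six Saxenda entries is "BMI not measured within 6 months before date of first prescription". Section 8.7.2 repeats the entry under its own outside-label heading, with a number and a proportion.

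Section 8.7.2 also states: "The main analysis will be to estimate the proportion of prescriptions outside label among" Saxenda or Victoza patients. It adds: "The proportion of each of the forms of prescription outside label will be described". The list is the only definition of outside label in the protocol, so the overall proportion has to be built from it.

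Two other places treat the same patients differently:

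- Section 7.1 quotes the indication. It turns on the initial BMI value, with a comorbidity condition in the overweight band, and does not say how recent the record must be.
- Section 7.3 makes "Number of patients with BMI not measured within 6 months before date of first prescription" a category of the primary endpoint, beside the measured BMI bands, and does not call it outside label.

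On data capture, Section 8.3 and footnote 5 of Table 1 limit baseline weight and BMI to the latest recording in the 6 months before first prescription. Section 8.9 says: "Data collection will reflect routine clinical practice rather than mandatory assessments at prespecified time points".

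**The concern.** A patient without a BMI in the window may be within or outside the indication; the chart does not say which. The plan nevertheless puts every such patient in the outside-label numerator. A patient whose clearly qualifying BMI was recorded seven months before first prescription would be scored outside label.

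The study was requested by the regulator (Section 6) to describe how the products are used, and this proportion is its main estimate. Scoring unknown as outside label can only push it up. Section 8.7.2 also plans to describe patients prescribed according to the SmPC. If that group is formed as the complement of the outside-label list, patients without a recent BMI drop out of it too.

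**Working it through.** **The plan's own figures.** The only numerical design figure is the number of patients (Section 8.2.1): 2 × (25 + 25) + 2 × (75 + 75) = 400, as stated. The full study has 2 × 75 = 150 Saxenda patients. The protocol gives no expected outside-label rate and no expected share without a BMI, so both are assumptions here.

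**BMI component alone.** Let m be the share of Saxenda patients with no BMI in the window and p the share outside the BMI indication among those measured.

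- As the plan scores it: p(1-m) + m.
- Among measured patients: p.
- Shift: m(1-p), which is positive whenever m > 0 and p < 1.
- Bounds over all Saxenda patients: p(1-m) if every unmeasured patient is within label, and p(1-m) + m if every one is outside. The plan's figure is therefore the worst-case bound reported as the estimate.

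Example with n = 150, p = 10%, m = 20%: 30 patients have no BMI, 120 are measured, and 12 of those are outside label.

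- As scored: (12 + 30)/150 = 28.0% (95% Wilson interval 21.4% to 35.7%).
- Among measured: 12/120 = 10.0% (5.8% to 16.7%).
- Bounds: 12/150 = 8.0% to 42/150 = 28.0%.
- Of the 42 patients counted as outside label, 30 (71%) have no BMI record.

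Scored proportion over the assumed range, from p(1-m) + m:

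| m | p = 0% | p = 10% | p = 20% |
|---|---|---|---|
| 5% | 5.0% | 14.5% | 24.0% |
| 10% | 10.0% | 19.0% | 28.0% |
| 20% | 20.0% | 28.0% | 36.0% |
| 40% | 40.0% | 46.0% | 52.0% |

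The shift runs from 4 points (p = 20%, m = 5%) to 40 points (p = 0%, m = 40%).

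**Composite.** The list also covers dose escalation, the stopping rule and concomitant GLP-1 receptor agonists. Let u be the share outside label on any form other than missing BMI. The scored figure is u(1-m) + m and the shift is m(1-u). With assumed u = 40% and m = 20%, the composite is 0.40 × 0.80 + 0.20 = 52% against 40%, a shift of 12 points. If Saxenda and Victoza are pooled with equal weight (150:150), the shift is 12 × 0.5 = 6 points.

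**The case against.** The strongest defence is that the information is not hidden. Each form is reported separately, and Section 7.3 counts these patients as their own category, so the primary-endpoint counts are unaffected and a reader can isolate the missing-BMI group. This stands, and it lowers the severity. It does not correct the overall figure: one patient can meet several forms, so the composite without this category cannot be rebuilt from the separate counts.

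A second defence is that the category captures prescribing without checking BMI. That is worth knowing and justifies keeping the count. But a chart review cannot separate it from a BMI recorded elsewhere or recorded earlier than the window, and neither of those places a patient outside the indication.

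Third, the pilot examines variable availability and quality and may lead to refinements (Section 8.1.1), missing data are followed up, and data are sought from other practices (Section 8.9). These steps may reduce m but leave the classification as it is. A SAP could add bounds, but it cannot use older values that the protocol does not collect.

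A reader might infer more than the documents support:

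- That Section 8.7 contradicts the list, because it refers to "number and proportion of patients with observed (non-missing) data for categorical variables". That sentence describes participant characteristics, and having no BMI in the window is itself a defined category.
- That a missing 16-24 week weight or dose is exempted while a missing BMI is penalised. The protocol gives a fallback for a missing weight, but does not say how an unrecorded weight or dose is classified. Silence is not an exemption.
- That the bias will differ between general practitioners and specialists. No missing-BMI rate is given for any setting.
- That the headline is mainly a measure of chart completeness, or that it counts misuse. The first depends on an unknown m; the second is not the protocol's term.

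**Conclusion.** The point holds as a classification error in the main analysis: unknown BMI status is scored as outside label, against the indication in Section 7.1 and the neutral count in Section 7.3. The direction is certain for any m > 0, unless every unmeasured patient is in fact outside label.

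The size rests on assumed rates. For the BMI component, p = 10% and m = 20% give 28% against 10%. A reader might carry that 18-point gap straight over to the headline. The documents do not support this, because the other forms dilute it to m(1-u) and pooling with Victoza would roughly halve it again. The 10% is also not a proven truth: it assumes that unmeasured patients resemble measured ones, which is why bounds are needed. Because each form is reported separately, this is a should-fix.

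**What to change.** 1. In Sections 8.3 and 8.7.2, move the missing-BMI entry out of the outside-label list into a category such as *BMI label status not assessable*.
2. Report the main proportion among assessable patients. Add two bounds over all Saxenda patients, setting the non-assessable first to within label and then to outside label. In both bounds, a patient without a BMI who is outside label on another form stays counted for that form.
3. Keep the separate count already in Section 7.3 as a description of recording practice.
4. Extend abstraction (Section 8.3 and Table 1, footnote 5) to the last weight or BMI before first prescription, with its date, when none lies in the 6-month window. Use it in a sensitivity analysis.

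The cost is one extra abstracted field where an older value exists, a few table rows, and wording changes. Step 4 has to be in the CRF before abstraction begins; the other steps change definitions and reporting only.
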